We will use a mixed-methods randomized controlled trial to evaluate the longitudinal impact of the STEADI protocol. See Table 1. We will study STEADI patients, patients who have received STEADI RA and fall prevention recommendations at OHSU Internal Medicine and Geriatrics. We will have two-groups. The control group participants will only receive study measurements at baseline, 3-, 6-, and 12-months baseline assessment. The intervention group will receive all the same measurements as the control group, and in addition, receive MI-based communication about fall prevention at eight occasions during the 6-month period. MI is an evidence-based communication approach for various health behavior change, however, it has not been widely applied to fall prevention interventions. Our preliminary feasibility trial with inpatients has demonstrated effectiveness of MI on fall-related patient outcomes. This protocol will test the effectiveness of MI with outpatients.

Since COVID-19 pandemic occurred in March 2020, the OHSU internal medicine clinic has limited in-person patient care hours and patients are not being routinely screened for fall risks using the STEADI protocol, impacting the study implementation. As patient-care situations are unpredictable at this time, we have following modification plans to the study protocol. Major changes are listed below and described in relevant sections of this protocol.

- 1) Identification and screening of STEADI patients using healthcare records of the past year. This will be in addition to recruitment of patients who are seen at the clinic for STEADI FRA/clinic visit as originally included in this protocol.
- 2) Addition of at-home visits (video, phone, or in-person) in place of in-person study office visits.
- 3) Changes to ensure safety of study office visits once these visits are possible.
- 4) [ADDED 7/14/20] Modification to use the information sheet for participant consent.
- 5) [ADDED 7/22/20] Details about exclusion criteria.

We request modification to the protocol as we uncovered that more than half of potentially recruitable participants did not receive fall prevention recommendations, thus because ineligible for the study.

Table 1. Study overview

	Baseline	1 wk, 1 & 2 m	3 m	4 & 5 m	6 m	12 m
Study time points	T0	T1, T2, T3	T4	T5, T6	T7	T8
Study encounter type	Visit ⁺	Phone/video	Phone	Phone/video	Visit ⁺	Phone/video
Intervention group only						
MI Intervention ^E	#1	#2, 3, 4	#5	#6 & #7	#8	

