determine their eligibility. If they meet all of the inclusion criteria, a study visit at OHSU or their home will be scheduled. This visit will be scheduled within 3 months of the initial clinic visit. The study flier will be posted at the clinic to inform participants about a potential call from the study team.

[COVID-related changes]

Since the COVID-19 pandemic is unpredictable, the study will include retrospective screening approach in addition to currently proposed prospective approach. We propose to contact patients who received STEADI FRA/clinic visit in the past (April 1st 2019-March 31st, 2020). We will review EPIC to identify these patients. We will explore all primary clinic services and locations where patients are expected to receive STEADI FRA.

[Clarification about the study exclusion criteria]

Before the recruitment call is made, study staff will review EPIC for any documentation of cognitive assessment. If the patient has a diagnosis of dementia (any type), their record will be reviewed for cognitive assessment scores and determination will be made about exclusion. If the results of cognitive assessment are documented within a year, and scores indicate normal cognition or mild cognitive impairment, no further assessment will be necessary. If there are no cognitive assessments conducted within the timeframe or results are variable, the study team will conduct a cognitive assessment during the recruitment interview using 6-item Callaham tool (<https://pubmed.ncbi.nlm.nih.gov/12218768/>). If the participant meets the cut off three or more errors, participant will not be able to participate in the study. During the recruitment call, the study staff will also ensure that the potential participant meets the following criteria: participant is able to converse audibly and coherently in English, and able to receive study phone calls, is willing to work with the study to set up video or in-person visits, and are ambulatory with or without assistive device use.

Thus, the study exclusion criteria are:

- Cognitively impaired patients as defined by Mini-Cog≤ 2 (<https://mini-cog.com/mini-cog-instrument/scoring-the-mini-cog/>), or SLUMS<19.5/<21.5 (no high school education/high school education), MMSE <26.5/<27.5; (no high school education/high school education) (<https://www.ncbi.nlm.nih.gov/pmc/articles/PMC5395300/>), MOCA <16 (<https://www.ncbi.nlm.nih.gov/pmc/articles/PMC6247398/>), or 3 or more errors on 6-item Callaham tool

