Study measurements. Several standardized study tools will be used at baseline, 3-months, 6-months, and 12-months after the benchmark STEADI clinic visit. The study domains and measurement tools are summarized in Table 2. The primary study outcome measures are: patient engagement with fall prevention recommendations (medication, exercise, blood pressure, vision, and environment), fear of falling, and fall prevention behaviors. The study will create, pilot test, and use the Fall Prevention Patient Engagement Scale created for the study to measure frequency and uptake of STEADI recommendations. Falls Self-Efficacy Scale-International (FES-I), a 16-item scale, is widely used to measure levels of concern related to preventing falls. Higher FES-I scores have been positively correlated with decreased activities, future falls, and injury. The 24-item version of Fall Behavioral Scale (FAB), will be used to capture patients' daily activities to prevent falling. FAB measures frequency of protective strategies to prevent falling and risky behaviors that facilitate a fall. Secondary study measures include physical function, patient activation, and fall rates. All participants will mail-in monthly fall calendar, the gold standard to capture fall rates. The chart reviews will be used to capture health status and other patient data.

[COVID-related change]

We will add a modified recruitment approach, to recruit patients who had the STEADI FRA/clinic visit up to a year ago. This clinic visit is when participants receive fall risk assessment and fall prevention recommendations. Since the duration between the time that they receive fall prevention recommendations and the initiation of the study could vary as much as a year, 1) we will add questions to assess what changes have taken place related to fall prevention since the clinic visit within Fall Prevention Patient Engagement Scale: pre-enrollment), 2) we will review STEADI recommendations at the baseline visit with all participants to refresh participants' memory on clinic recommendations, and 3) we will analyze the impact of the length of time between the STEADI clinic visit and study outcomes.

We propose to have multiple options available for baseline and 6-month study visits in addition to in-person study office visits as originally planned. This will allow for flexibility in participants' involvement with the study. We will have options for at-home virtual (phone or video) and in-person visits.

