Intervention group. The intervention group participants will receive Motivational Interviewing (MI) communication about fall prevention during the 12-month study period. Interventionists will facilitate MI sessions using the MI guide (baseline version outlined in Table 32) and a participant handout, “Menu of Options for Fall Prevention,” which outlines potential topics for the discussion. MI sessions will be held at baseline, 1-week, then monthly for 6 months. MI sessions are mostly conducted via phone except the baseline and 6-months visit. The MI guide and the handout were created and tested by the study team through a feasibility study. Each MI session is targeted to be 15-minutes long. From our prior study we determined that this duration is most appropriate, short but possible to impact patient engagement with fall prevention. All of the study encounters will be audio recorded with participants’ permission and study encounter notes will be completed.

[COVID-related changes]

MI sessions will be completed via phone or video depending on the availability for the participant. Although delivery methods differ slightly, the goal of this intervention will be the same.

Table 3. Motivational Interviewing intervention guide (template for baseline study visit)

Basic approach	
Ask for permissions to discuss certain topics, use OARS (Open-ended questions, Affirming, Reflections, and Summarizing), and evoking as appropriate (make statements or ask questions to provoke alternative thinking about a situation)	
MI intervention based on readiness to change	

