
Establish rapport. Identify patient values and goals.
 
Observe patients' responses toward "Menu of Options for Fall Prevention" handout.*
 
Identify readiness to change & tailor the conversation based on the readiness.
	
Pre-contemplation: Focus on building trust (use OARS) and keeping the conversation going about fall prevention. Potentially focus on participant's strengths and goals in life. Ask permissions. Evoke as appropriate.
 
Contemplation & Ready: Focus on building trust (use OARS). Ask for permission. Evoke as appropriate. Identify one behavior that the participant is OK to talk more about (Behavior A). Go to STEP #.
 
Action & Maintenance: Focus on affirming, and adding more to the fall prevention activities. Anticipate future situations, or challenging situations (when sick). Identify one behavior that the participant is interested in talking more about (Behavior A). Go to STEP #.
 
STEP #: If behavior change topic has been identified...
 
 Identify goals with this behavior Identify readiness to change (importance and confidence) to change Identify a specific plan to move toward the goal Identify barriers and facilitators for change Identify participant's commitment level to change

Notes: "Menu of Options for Fall Prevention" handout includes 20 conversation topics about mobility and health goals, fall risks, and fall prevention strategies. Follow-up MI interventions will assess changes related to Behavior A and discussion related to new behaviors (B, C, D...) to change.
	

Control group. Participants in this group will have their study measurements at baseline, 3-months, 6-months, and 12-months after the benchmark STEADI clinic visit. They will not receive study MI intervention calls after fall prevention recommendations are given at the clinic. If the participants have any questions about fall prevention during the data collection, study staff will relay this message to the clinic staff.

[COVID-related changes]

Study physiologic measurement at baseline and 6-months will be conducted in the same manner (i.e., at-home).

Data and Specimens

Source of materials. Research data used specifically for research purposes will be obtained directly from participants in self-report surveys and physical function tests, and from EHR chart review.

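### Study measurements and Control group date the 3-, 6- and 12-month outcomes from the STEADI clinic visit, whereas Table 1 runs them from study baseline

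*Combined protocol and SAP*

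**What the plan says.** Two sections tie follow-up to the clinic visit. Study measurements, which also names the primary outcomes, says that "Several standardized study tools will be used at baseline, 3-months, 6-months, and 12-months after the benchmark STEADI clinic visit". The Control group section says: "Participants in this group will have their study measurements at baseline, 3-months, 6-months, and 12-months after the benchmark STEADI clinic visit". The protocol describes that clinic visit as the clinical encounter at which fall risk was assessed and advice given. It is a separate event from study enrolment, and an earlier one.

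The rest of the protocol counts from study baseline:

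- Table 1 labels Baseline as T0. It places the 3-month measures (T4) with MI #5 and the 6-month measures (T7) with MI #8, on one time axis for both arms.
- The Intervention group section says "MI sessions will be held at baseline, 1-week, then monthly for 6 months". The opening summary times MI from the initial visit, and the COVID-related text on sessions makes MI #1 part of the baseline visit.
- Design describes the controls thus: "The control group participants will only receive study measurements at baseline, 3-, 6-, and 12-months baseline assessment". The sentence is garbled, but it refers to baseline and not to the clinic visit. Of the other arm it says: "The intervention group will receive all the same measurements as the control group".

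On the gap between the two events, Recruitment methods says of the study visit: "This visit will be scheduled within 3 months of the initial clinic visit". For retrospective recruits it says: "We propose to contact patients who received STEADI FRA/clinic visit in the past (April 1st 2019-March 31st, 2020". The COVID-related change under Study measurements accepts that the gap may reach a year.

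**The concern.** The time frame of every questionnaire outcome, including all three primary ones, is stated in two ways that conflict for anyone not enrolled on the day of the clinic visit. If the clinic-visit rule were followed, the label on an outcome would no longer say how much MI came before it. A 6-month result would mix participants near the end of the course with participants halfway through it, and for long lags some assessments would be due before enrolment. A reader of the results could not tell from the protocol which clock the reported time points use.

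**Working it through.** The protocol gives no figure to reproduce here; the check is timeline arithmetic.

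**Inputs**
- MI times in months from baseline: 0, 0.25, 1, 2, 3, 4, 5, 6, which is eight sessions (Table 1; Intervention group; one week taken as 0.25 month).
- Nominal outcome times m = 3, 6, 12 (Study measurements).
- Lag d from clinic visit to baseline: 0 to 3 months for prospective recruits (Recruitment methods); up to 12 for retrospective recruits (Study measurements, COVID-related change).

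**Formulas**
- On the clinic clock, outcome time from baseline = m − d.
- Sessions received = number of MI times at or before m − d if a same-day session counts, or strictly before m − d if MI follows measurement. The COVID-related text uses the second order at baseline. Both counts are shown as same-day counted / strictly before.

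**Prospective stream, clinic clock**

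| d | 3-month outcome: months from baseline; sessions | 6-month outcome: months from baseline; sessions | 12-month outcome: months from baseline; sessions; months since MI #8 |
|---|---|---|---|
| 0 | 3; 5/4 | 6; 8/7 | 12; 8/8; 6 |
| 1 | 2; 4/3 | 5; 7/6 | 11; 8/8; 5 |
| 2 | 1; 3/2 | 4; 6/5 | 10; 8/8; 4 |
| 3 | 0; 1/0 | 3; 5/4 | 9; 8/8; 3 |

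On the baseline clock the d = 0 row applies to everyone, whatever the lag.

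For any d > 0, 6 − d < 6, so the 6-month outcome comes before MI #8. The strict count is 7 of 8 even at d = 0, so that one-session shortfall reflects the order of events within the visit and not the anchor. The anchor's own effect is the difference from the d = 0 row. At d = 1, 2, 3 this is 1, 2, 3 sessions for the 6-month outcome and 1, 2, 4 for the 3-month outcome, under either count.

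**Longer lags, clinic clock (m − d for m = 3, 6, 12)**
- d = 6: −3, 0, 6
- d = 9: −6, −3, 3
- d = 12: −9, −6, 0

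For d > 3, 3 − d is negative: the 3-month outcome is due before baseline.

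**How far this reaches into the retrospective stream**

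The latest clinic visit in that window is 31 March 2020. The modification list in Design includes "ADDED 7/14/20] Modification to use the information sheet for participant consent". From 31 March to 14 July 2020 is 30 + 31 + 30 + 14 = 105 days, and 105 / 30.4375 = 3.45 months. A retrospective recruit consented on or after 14 July 2020 therefore has a lag above 3 months, and the clinic-clock 3-month date has already passed at baseline. The date on which retrospective contact began is not stated, so this covers only consents from 14 July 2020 on.

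**The case against.** The best answer is that the clock is already fixed. Table 1 gives one coherent schedule for both arms, the summary gives everyone a baseline and a 6-month study visit, and the Analysis section speaks of 3-, 6- and 12-month study encounters. To follow the clinic-visit phrase, staff would have to detach the measurements from the encounters that Table 1 pairs with MI #5 and MI #8, and for long lags they could not follow it at all. The phrase is also loose: grammatically it governs baseline too, which has no fixed interval from the clinic visit. Finally, the document is dated January 2023 and its December 2022 addition describes 101 participants already allocated to MI, so rewording alters little conduct.

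Much of this stands. Staff probably used Table 1, and the table above describes a literal reading, not observed conduct. But the rule is stated twice, once in the section that defines the outcomes. At prospective lags below 3 months it can be carried out, so nothing would stop a literal reader. The 3-month allowance also sits outside the COVID-related changes, so those changes widened the conflict but did not create it. The planned lag analyses and the baseline review of recommendations do not re-anchor follow-up.

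Two stronger readings are tempting.

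- A reader might infer that controls are timed from the clinic visit and the MI arm from baseline, which would bias the comparison. The documents do not support this: Design gives both arms the same measurements, and the Study measurements sentence covers everyone. Randomization should also balance the lag between arms in expectation.
- A reader might argue that the planned lag analysis makes sense only on the baseline clock, which would prove the clinic anchor a slip. Analysis defines the lag as running from the STEADI assessment to the baseline visit. That varies between participants on either clock, although on the clinic clock it would be mixed with MI exposure.

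**Conclusion.** The outcome time frame is wrong as written in Study measurements and Control group. It is an internal inconsistency with Table 1 and the MI schedule, and it deserves correction because it concerns the primary outcomes. At the 3-month prospective maximum, literal use moves the outcomes to 0, 3 and 9 months after baseline. The 6-month outcome then follows 5 of 8 sessions (4 if MI comes after measurement), against 8 (or 7) as Table 1 intends. Above 3 months the 3-month outcome cannot be done.

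These sizes assume that MI keeps to its schedule from baseline and that the clinic-visit rule is applied as stated. The documents give no evidence that anyone was measured that way and no basis for alleging bias between arms.

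**What to change.** In Study measurements and in Control group, replace the closing reference to the STEADI clinic visit with: after the study baseline visit. Apply this to both arms and both recruitment streams, as in Table 1. Outcomes then fall 3, 6 and 12 months after T0 at any lag, with MI #5 and MI #8 at the first two. Since allocation is well advanced, the reports should also state which clock was used.

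If any participant was measured on the clinic clock, report actual time from baseline to each assessment by arm and run a sensitivity analysis using actual time.

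The cost is one phrase in each of two sections, with no added visits, participants or measures. The extra analysis is needed only if the clinic clock was used for someone.

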Intervention and control groups						
Self-report measures*	X		X		X	X
Physiologic measures**	X				X	
Fall rates (mail-in)	X	X	X	X	X	X
Notes: Self-report measures* : Fall Prevention Patient Engagement Scale, Fall Efficacy Scale International, Fall Behavioral Scale, Patient Activation Measure. Physiologic measures** : Timed Up and Go, 30-Seconds Sit-to-Stand, & 4-Stage Balance Test. E : Documented in study encounter notes (narrative descriptions of behavior change topic, behavioral goal, readiness to change, importance, confidence, commitment, barriers & facilitators for change, change from the last study encounter, satisfaction).						
wk : week, m : month						
⁺ : Visits: includes 3 options: in-home (virtual and in-person) & study office in-person visits						

Study population

Number of subjects. We estimated the sample size based on the key primary outcome measure, fear of falling as measured by FES-I, which has a reported effect size ranging from .03 to .42 depending on the setting and the type of intervention. The PI's MI intervention with inpatients found an effect size of .31 with high fall-risk inpatients. Using the power of 80% and alpha of 0.05, we need a minimum of 120 participants for an independent t-test calculation. To account for attrition, we aim to enroll 250 participants.

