We will conduct interviews with maximum of 20 participants to understand study participants' experience with the study. This interview will be consistent with the current study protocol in which study staff interacts with participants via phone, recorded, transcribed, and analyzed.

Participants will be selected to represent control and intervention groups and based on data collected during the study. Participants' interest in this evaluative interview will be asked by phone or email. Participants will receive the information sheet about this study evaluation interview along with research questions prior to the interview. Each interview will be about 30-45 minutes. The interview guide, information sheet, and interview questions are submitted to IRB along with this modification request.

Table 2. Study domains and measurement tools

Study Domains	Measurement tools
Individual and unique patients Cognition Emotional barriers* Values and goals* Physical and cognitive limitations* Physiologic measures (S)	Mini-Cog Encounter note (narrative; MI group only) Encounter note (narrative; MI group only) Encounter note (narrative; MI group only) 30-Second Chair to Stand Test, 4-Stage Balance Test, & Timed Up and Go Test
Fall prevention recommendations Motivational Interviewing*	Chart review Recorded MI sessions & encounter notes (narrative; MI group only)
Patient engagement measures Self-reported engagement with fall prevention recommendations (P) Commitment to fall prevention recommendations*	Fall Prevention Patient Engagement Scale* Encounter notes (narrative; MI group only)
Fall-related outcomes Fear about falling (P) Fall prevention behaviors (P) Patient activation (S) Fall rates (S)	Fall Self-Efficacy International Fall Behavioral Scale Patient Activation Measure Fall incidences by calendar month

Notes: (P) Primary outcome measure. (S) Secondary outcome measure. (MI) pertains only to the MI group. ***Fall Prevention Patient Engagement Scale** is an original tool created for the study and includes frequency of engagement with the recommendations. **Others:** Chart review will gather age, gender, diagnosis, and medications at baseline.

Safety regarding in-home STEADI physiologic assessment is described in the Data and Specimens section.

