Staff will wear mask and practice hand hygiene. Work hours are variable depending on the study status and the preference of the worker. It is expected to be 6-15 hours/week. The hours will not exceed 30 hours/ week.

-
- Study staff will disinfect surface touched by participant between the visits.
- If possible, windows will be open for improved ventilation.
- The study visit will be conducted one participant at a time ensuring 6-feet distance between the staff and participant except to ensure safety during physiologic assessments.

Analysis

First, we will examine the following: recruitment, retention (numbers contacted, consented, screened out, and completed 70% of the intervention), and reasons for not participating or withdrawing. We will ask participants about challenges related to participation at 3-month, 6-month, and 12-month study encounters. Second, to determine the primary impact of MI as compared to a standard care group, patients' engagement with fall prevention recommendations (medication, exercise, blood pressure, vision, and environment), fear of falling, and fall prevention behaviors will be assessed quantitatively. The secondary impact will be measured by physical functions, patient activation, and fall rates. Descriptive statistics will be used to identify distributions and frequencies of the study outcomes. Third, we will use qualitative approach to determine how MI engages individuals in fall prevention behaviors. We will use quantitative findings to purposefully select the sample for the qualitative analysis. We will review the transcribed MI sessions and analyze the findings.

[COVID-related changes]

We will conduct additional analyses to evaluate 1) how the time between the STEADI FRA and the baseline study visit influence the recall of the FRA recommendations, engagement with fall prevention activities, and engagement with the study, 2) the difference in study outcomes between virtual vs. in-person visits, and 3) the impact of COVID-19 on fall prevention.

Privacy, confidentiality, and data security

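### Three unranked primary outcomes at three follow-up times, with no primary time point, testing order or success rule, in a trial sized on FES-I alone at alpha 0.05

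*Combined protocol and SAP*

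**What the plan says.** **Three primaries.** Study procedures (Study measurements) says: "The primary study outcome measures are: patient engagement with fall prevention recommendations (medication, exercise, blood pressure, vision, and environment), fear of falling". The sentence goes on to fall prevention behaviors, measured by FAB. Table 2 marks the same three with (P) and does not rank them. The Analysis section repeats them as the primary impact, ending: "fear of falling, and fall prevention behaviors will be assessed quantitatively".

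**One sizing outcome.** Number of subjects says: "We estimated the sample size based on the key primary outcome measure, fear of falling as measured by FES-I". At 80% power and alpha 0.05 it concludes: "we need a minimum of 120 participants for an independent t-test calculation". Enrolment is set at 250, and Randomization gives 125 per arm.

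**Analysis method.** The only method the Analysis section names for the outcomes is this: "Descriptive statistics will be used to identify distributions and frequencies of the study outcomes". The t-test in the sample-size sentence is the only between-group test in the document.

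**Timing.** Table 1 starts at study baseline (T0) and places the self-report measures at baseline, 3, 6 and 12 months. Study measurements counts differently: "Several standardized study tools will be used at baseline, 3-months, 6-months, and 12-months after the benchmark STEADI clinic visit". The Control group paragraph uses the same clinic-visit anchor. Recruitment methods puts the first study visit within 3 months of the clinic visit. The COVID-related change then allows a gap of up to a year.

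**The concern.** The plan does not say which result, at which time, decides whether MI worked. Three outcomes at three times give nine candidate results. The ranking implied by the sample-size paragraph does not reappear where outcomes are defined or analysed, and Study measurements and Analysis both list engagement first. Mixed results would have no agreed reading, and a favourable result on one scale at one visit could be presented as the primary effect.

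The two time anchors add to this. Even FES-I at 6 months is not one defined quantity while one part of the plan counts from the clinic visit and another from baseline.

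**Working it through.** **The plan's own figure.** The only stated figure is the minimum of 120. It is not reproduced from either effect size that could plausibly have been used: two-sided, d = .31 needs about 164 per arm (328 in all) and d = .42 about 90 per arm (180 in all). That is a separate matter. What follows uses only alpha 0.05, three outcomes and 125 per arm.

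**Any-one-positive rule, one time point.** Assume three two-sided tests at 0.05 and no true effect. If independent, the rate is 1 - .95³ = .143. With a common correlation ρ it is 1 - E[p(W)³], where W is standard normal and p(w) = Φ((1.96 - √ρ·w)/√(1-ρ)) - Φ((-1.96 - √ρ·w)/√(1-ρ)). The documents give no correlation, so ρ is an assumption:

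| ρ | 0 | .3 | .5 | .7 | .8 | .9 |
|---|---|---|---|---|---|---|
| Any one positive | 14.3% | 13.6% | 12.5% | 10.9% | 9.8% | 8.4% |

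**Any-one-positive rule, all nine outcome-by-time tests.** Simulation gives about 18% to 33%, for assumed correlations of 0 to .8 between outcomes and .5 to .8 over time.

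**All-three rule.** With no true effects the rate is .0001 (ρ = 0) to .014 (ρ = .8). If one or two outcomes truly respond, a null outcome must still reach 0.05 by itself, so the rate cannot exceed 5%.

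**Power for FES-I.** Read the plan's .31 as a standardised mean difference, with n per arm and no dropout. Approximate power is Φ(d·√(n/2) - z); the percentages below are from the exact t calculation. The critical z is 1.960 at 0.05 and 2.394 at 0.05/3, the first Holm step.

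- Unadjusted, n = 125: .31 × √62.5 = 2.451. Power is 68% at 0.05 and 52% at 0.05/3.
- Baseline-adjusted, assumed baseline-to-follow-up correlation .5: effective d = .31/√(1 - .25) = .358, and .358 × √62.5 = 2.83. Power is about 80% and 66%.
- Unadjusted, n = 101 in both arms (Appendix 2 reports 101 allocated to MI; the same number in control is an assumption): 59% and 42%.

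If all three outcomes responded at .31 (an assumption), unadjusted Holm would detect at least one with 67% (ρ = .8) to 89% (ρ = 0).

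**Time anchor.** With a lag of L months from clinic visit to baseline, a 6-month measure counted from the clinic visit falls 6 - L months after baseline. For L = 0 to 3 that is 6 down to 3 months. For L above 6 no such date exists after enrolment, so the wording cannot apply to participants recruited up to a year after the visit.

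**The case against.** **FES-I is already the deciding outcome.** A reader might infer this from the sample-size paragraph, which singles it out and attaches the only named test. That would bring the error rate back to 5% at one named time point. But the paragraph names no time point and no decision rule, and the outcome section, Table 2 and Analysis all give the other two scales the same standing. The inference is reasonable; the plan does not state it.

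**The inflation is hypothetical.** This stands in part. The 10-14% needs a success rule the plan does not state and correlations it does not give, so a reader should not take it as the trial's actual error rate. The missing rule is a defect whatever the correlation.

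**Follow-up would precede enrolment.** Subtracting a 12-month lag from 6 months suggests this, but it is not a live reading. Table 1, the introduction and the Intervention group section all work from study baseline. The plan also recognises the variable lag and intends to analyse it. What stands is wording in two places that must be reconciled with Table 1.

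**Six months is not the only candidate.** This stands. Table 1 puts the last MI session (#8) at 6 months, but the Design and Benefits text stresses longitudinal and long-term impact, which could favour 12 months. The introduction and the Intervention group section also mention a 12-month period for MI alongside monthly sessions for 6 months, and those statements should be reconciled. At 6 months, the order of the self-report measures and MI #8 is not fixed.

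**Engagement should not be demoted.** This also stands. It is in the trial's title and comes first in two of the lists, so making FES-I the sole primary is the sponsor's choice and does not follow from the defect.

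**Conclusion.** The point holds. Three outcomes are primary without rank, the trial is sized on one of them at 0.05, and nothing in the plan says which result at which time decides. Under an any-one-positive rule the false-positive rate at one time point would be about 10-14% for assumed correlations of 0 to .8 (8.4% at .9). Under an all-three rule it would not exceed 5%. The conflict over the time anchor is real but is one of wording. This should be corrected; it does not by itself invalidate the trial.

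A reader might infer from Appendix 2 and the 1/19/23 interview update, which select participants using collected study data, that between-group results had already been seen. Neither text shows that.

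**What to change.** 1. In Study measurements and the Control group paragraph, state that 3, 6 and 12 months are counted from study baseline, as in Table 1.
2. Name one primary time point. Six months from baseline is a reasonable option because Table 1 ends MI there; if it is chosen, fix the order of the self-report measures relative to MI #8. The sponsor may prefer 12 months, given the long-term aim.
3. Compare arms as randomised, by linear regression of the score at that time on arm and the baseline value of the same scale, in place of the unadjusted t-test. Baseline FES-I and FAB are taken in the first baseline session, before MI #1 in the third, so the covariates are available.
4. Choose one rule. Either keep all three as primary with Holm across them at that time point, or, if the sponsor confirms the priority in the sample-size paragraph, make FES-I the single primary and relabel the other two as secondary in Study measurements, Table 2 and Analysis.
5. Report every other outcome-by-time result with an estimate and 95% confidence interval.

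**Cost.** One dated amendment or a short SAP, with no new data. Holm lowers unadjusted power for FES-I from 68% to 52% at its first step; baseline adjustment recovers some of this, and attrition lowers all these figures. Choosing FES-I alone means engagement and FAB cannot support a primary claim. Date the change before between-group results are seen; if they have been seen, report the hierarchy as post hoc.
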